#### 5.2. Handling of Dropouts, Missing Data, and Outliers

#### 5.2.1. Handling of Missing Efficacy Data

For Part A, missing efficacy data will not be replaced for the primary efficacy analysis.

For sensitivity analysis of the efficacy endpoints in Part A (efficacy endpoints of NT-proBNP, BNP, and urine and plasma cGMP), inference will be done using mixed-effects models repeated-measures, which assumes that missing outcomes are missing at random (MAR).

\* Except for plasma cGMP and 6-hour urine collection cGMP where baseline is assessed on Day -1. See Section 5.1.2 for details on the baseline definition.

### **5.2.2.** Handling of Missing Safety Data

In general, missing clinical laboratory data, vital signs, and ECG data will not be imputed. Adverse event imputations for missing severity or relationship are given in Section 6.7.2. Unknown or partial medication and AE date imputations are given below and to be used only for the assessment of prior / concomitant status for medications and treatment-emergent status for AEs.

# **5.2.3.** Handling of Partial and Missing Dates for Adverse Events, Prior / Concomitant Medications

Missing or Partial Adverse Event and Prior / Concomitant Medication Start Dates

Missing and / or incomplete dates for medications and AEs are imputed in a manner resulting in the earliest onset or the longest duration during the Treatment Period, whilst ensuring that the start date does not occur after the stop date. The stop date will not be imputed if the medication or AE is "Ongoing". Technically, this will be done as follows:

For a missing / incomplete start date / time the earliest date / time of the following will be imputed:

- The later date of: the earliest possible start date / time, and the date / time of first dose of treatment.
- The latest possible start date / time.
- The latest possible stop date / time.

For a missing / incomplete stop date / time the later date / time of the following will be imputed:

- The earlier date / time of the latest possible stop date / time and the date / time of last dose of treatment.
- The earliest possible stop date / time.
- The earliest possible start date / time.

Here, the earliest possible date / time is defined as:

- The date / time itself if available.
- The date / time of the first day of the month at 00:00hrs, if month and year are available but the day / time is missing.
- The date / time of the first day of the year at 00:00hrs, if year is available but day / time and month are missing.
- 00:00hrs on the day of informed consent, if the date / time is completely missing.

The latest possible date / time is defined as:

CONFIDENTIAL

CONFIDENTIAL
Protocol Reference: CRD-740-201

- The date / time itself if available.
- The date / time of the last day of the month at 23:59hrs, if month and year are available but the day / time is missing.
- The date / time of the last day of the year at 23:59hrs, if year is available but day / time and month are missing.
- 23:59hrs on the date of last known date on the study for the subject plus one year, if the date / time is completely missing.

# **5.2.4.** Handling of Plasma / Blood / Serum Concentrations that are Below the Lower Limit of Quantification

Plasma / blood / serum concentrations that are below the lower limit of quantification (BLQ) will be handled as follows for descriptive statistics:

- Values that are BLQ will be set to 0 for the calculation of summary statistics.
- Arithmetic mean or median values that are BLQ will be presented as 0.
- If any BLQ results (treated as 0) are in a series of summarized data, geometric mean and coefficient of variation (CV) % of geometric mean will be reported as not calculated (NC).

### 6. Statistical Methods

## **6.1. General Principles**

All data processing, summarization and analyses will be performed using Labcorp Drug Development's SAS Environment / Version 9.4 (or later) of the SAS® statistical software package.

The default summary statistics for quantitative variables will be the number of observations (n), mean, standard deviation (SD), median, minimum (min) and maximum (max), for those subjects with data.

For qualitative variables, the number (n) and percentage (%) of subjects with non-missing data per category will be the default summary presentation, and where appropriate and present, the number of missing values as a "Missing" category. Number of subjects in the analysis population will be used as denominator for percentages calculation, unless stated otherwise in TFLs mock shells.

All statistical comparisons will be made using one sided tests at the  $\alpha$ =0.025 significance level unless specifically stated otherwise. All null hypotheses will be of no treatment difference. All alternative hypotheses will be one-sided.

All laboratory test results will be received from the central laboratories, and the results will be provided in both standard internal (SI) and conventional units. For the TFLs, the results will be summarized or presented in International System of Units (SI) units. Refer to Appendix of the TLFs mock shells for the SI unit corresponding to each laboratory test. Refer to Appendix of the TLF shells for the precision level in which each laboratory test is reported by the central laboratories.

Specifications for table, figures and data listing formats can be found in the TFL shells specifications for this study. Please refer to "2. General Format Guidelines" section within TFL shells for more details on presentation of results.

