8.3. General Considerations

In general, data will be summarized with descriptive statistics for continuous endpoints, and frequency and percentage for categorical endpoints, unless otherwise specified. Percentages by

FINAL 10 AUG 2022 Page 53 of 73

CONFIDENTIAL Sponsor Reference: CRD-740-201

categories will be based on the number of subjects with no missing data (i.e., will add up to 100%).

Baseline will be defined as the last non-missing observation prior to first treatment intake, unless otherwise specified.

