# 3.1.2.5. Population-level Summary for Comparison between Treatment Conditions

The treatment effect will be quantified by the proportion of subjects who experience any AE, the proportion of subjects who experience any SAE and the exposure-adjusted incidence rates for AE and SAE in each treatment and dose level group.

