#### 4.7. Safety Analysis Population (SAF)

The Safety population will consist of all subjects who received at least one dose of CRD-740 or placebo. Subjects will be analyzed according to the treatment first received. The Safety population will be used as the primary safety population.

CONFIDENTIAL

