Adverse events will be summarized by treatment group and overall by dose period (Period 1, Period 2, Period 3, pooled Period 2 and Period 3, and overall) for Part A in the SAF.

- An overview of TEAEs including the number and percentage of subjects with at least one of each mentioned TEAE type:
  - o Any TEAE
    - Leading to discontinuation of study
    - Leading to discontinuation of study treatment
    - Leading to death
    - Mild
    - Moderate
    - Severe
  - Any study treatment related TEAE
    - Leading to discontinuation of study
    - Leading to discontinuation of study treatment
    - Leading to death
  - o Any serious TEAE
    - Leading to discontinuation of study
    - Leading to discontinuation of study treatment
    - Leading to death
  - o Any serious study treatment related TEAE
    - Leading to discontinuation of study
    - Leading to discontinuation of study treatment
    - Leading to death
- The number and percentage of subjects reporting each TEAE and the count of number of events will be summarized by SOC and PT for the following types of TEAEs:
  - o All TEAEs
  - o TEAEs Leading to Discontinuation of Study Treatment
  - o TEAEs Leading to Dose interruption
  - o TEAEs Leading to Study Withdrawal
  - TEAEs Leading to Death
  - o TEAEs by Maximum Severity
  - o TEAEs by Relationship to Treatment
  - o TEAEs by Relationship and Maximum Severity
  - Study Treatment related TEAEs
  - Study Treatment Related TEAEs Leading to Discontinuation of Study Treatment

CONFIDENTIAL

- CONFIDENTIAL
  Protocol Reference: CRD-740-201
- o Study Treatment related TEAEs Leading to Death
- Serious TEAEs
- o Serious TEAEs Leading to Discontinuation of Study Treatment
- o Serious TEAEs Leading to Dose Interruption
- Serious TEAEs Leading to Study Withdrawal
- Serious TEAEs Leading to Death
- Study Treatment Related Serious TEAEs
- Study Treatment Related Serious TEAEs Leading to Discontinuation of Study Treatment
- o Study Treatment Related Serious TEAEs Leading to Death
- o Study Treatment Related Serious TEAEs Leading to Study Withdrawal
- The number and percentage of subjects who died will be summarized by the primary reason of death (if available)

In the above summaries, subjects with more than one TEAE within a particular SOC are counted only once for that SOC. Similarly, subjects with more than one TEAE within a particular PT are counted only once for that PT.

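### The SAP's default percentage denominator departs, unrecorded, from protocol 8.3 and, unless the table shells override it, dilutes by-timepoint safety categories and later-period AE percentages

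*SAP*

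**What the plan says.** SAP 6.1 gives the default for qualitative variables: "Number of subjects in the analysis population will be used as denominator for percentages calculation". It allows one exception, "unless stated otherwise in TFLs mock shells", and provides for a Missing row where appropriate.

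Protocol 8.3 uses a different base. There, percentages by "categories will be based on the number of subjects with no missing data", so that the categories sum to 100%. SAP section 7 lists changes as small as the baseline rule for spot urine cGMP, but not this one.

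The default reaches the safety tables through these sections:

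- SAP 4.7: "The Safety population will consist of all subjects who received at least one dose of CRD-740 or placebo". A subject dosed once stays in this population whenever they stop.
- SAP 6.7.2: "Adverse events will be summarized by treatment group and overall by dose period". The periods are 1, 2, 3, pooled 2 and 3, and overall. No period-specific denominator is given.
- SAP 6.7.3, 6.7.5 and 6.7.6: laboratory shifts, CTCAE shifts, the investigator's ECG assessment and physical-examination abnormalities are percentages at each timepoint. No timepoint-specific denominator is given.
- SAP 5.1.4: for a subject who discontinues in Period 1 or 2, the last dose ends that period, so the subject has no later one.
- SAP 3.1.2.5: the primary safety estimand is summarised by "the proportion of subjects who experience any AE, the proportion of subjects who experience any SAE", together with exposure-adjusted rates, by treatment and dose level.

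**The concern.** A subject who stops in Period 1 cannot contribute an event to Period 2 or 3, but under the default still counts in the denominator for those periods. A subject with no ECG at Week 12 likewise counts in the Week 12 ECG denominator. Later percentages then come out lower than they were among the subjects actually observed.

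This matters mainly for reading Part A as a dose-ranging study. Escalation takes place at Day 15, so the diluted periods are those after escalation, while Period 1 is undiluted. Periods 1 and 2 each last two weeks and invite direct comparison within an arm. That comparison is distorted even if both arms lose the same share of subjects. (Period 3 lasts eight weeks, so its head-count percentage is not comparable with Period 1 in any case.)

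The SAP already adjusts for time at risk elsewhere. Exposure-adjusted rates divide by at-risk time (6.7.2), and compliance by period divides by days within the period (6.5). Only the head-count percentages lack a matching rule.

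**Working it through.** The documents state no figure that depends on the denominator, and the sample size was not set by a power calculation, so there is no plan figure to reproduce.

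**Inputs from the documents.** About 60 subjects at 2:1 (SAP 2.3), which gives 60 × 2/3 = 40 on CRD-740 and 60 × 1/3 = 20 on placebo. Withdrawals are not replaced (protocol 4.3.6).

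**Assumed inputs.** No attrition or event rate is given. Let d be the share of an arm not dosed in the period, or not assessed at the timepoint. I take d from 0 to 20% and a true percentage of 10% or 25% among those observed.

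**Formula.** Percentage shown = true percentage × (1 − d).

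**One arm, 40 subjects:**

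| d | Observed n | Shown if true 25% | Shown if true 10% |
|---|---|---|---|
| 0 | 40 | 25.0% | 10.0% |
| 5% | 38 | 0.25 × 0.95 = 23.8% | 9.5% |
| 10% | 36 | 9/40 = 22.5% (against 9/36 = 25%) | 9.0% |
| 20% | 32 | 8/40 = 20.0% (against 8/32 = 25%) | 8.0% |

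With the number observed as denominator, the result is 25.0% (or 10.0%) in every row.

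**Two arms, true 25% in both:**

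- 10% gone in each arm: 22.5% and 22.5%. No false difference.
- 10% on CRD-740, 5% on placebo: 22.5% and 23.8%, a false difference of 1.3 points (0.25 × 0.05 = 1.25).
- 20% on CRD-740, 5% on placebo: 20.0% and 23.8%, a false difference of 3.8 points (0.25 × 0.15 = 3.75).

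**Which tables are reached:**

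- By-timepoint laboratory shift, CTCAE shift, ECG assessment and physical examination: diluted by the share not assessed. These are categorical data, so protocol 8.3 applies directly.
- By-period adverse event head counts (Period 2, Period 3, pooled): diluted by the share never dosed in that period. The cause is the lack of an at-risk denominator.
- Exposure-adjusted rates (6.7.2): not affected, because a subject who stopped in Period 1 adds no time to Periods 2 and 3.
- Vital signs (6.7.4): not affected. Only continuous summaries are planned, and 6.1 computes those on subjects with data.
- Worst CTCAE grade and maximum QTc taken over all post-baseline visits: not affected in this way, because missing a later visit does not remove the subject.

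**The case against.** The strongest objection is that SAP 6.1 states only a default. The table shells can override it, and they may already set period and timepoint denominators. That stands: a reader might infer that every percentage in the report will be diluted, and the documents do not show this. They do show that the rule written in the SAP conflicts with the protocol and that the safety sections give no other.

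A second objection is that protocol 8.3 does not clearly govern adverse event incidence. Its rule concerns categories that sum to 100%, and a subject without an event is not missing. This also stands. It is tempting to call the by-period adverse event tables a breach of 8.3, but the text does not support that.

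Third, the primary safety analysis divides by at-risk time, and no statistical comparison of adverse events is planned. Both are correct. The proportions are one component of the estimand's summary, alongside rates that the default leaves intact.

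Fourth, stopping drug is not leaving the study. Protocol 4.3.3 encourages subjects to attend remaining visits and expects interruption or discontinuation to be rare, and SAP Table 3 uses data after discontinuation. By-timepoint tables therefore lose only subjects not assessed. A Missing row, where shown, would reveal this, and SAP 6.2 reports how many complete each period. These points reduce the likely size, but a Missing row would not reveal who had left before a by-period adverse event count.

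Finally, a denominator of subjects dosed in the period conditions on having reached it, so it does not give a randomised comparison either. That is a real, small drawback.

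**Conclusion.** The point holds as a minor one. The SAP default conflicts with protocol 8.3 for categorical data, and section 7 omits the change. Where the shells do not override it, the default multiplies by-timepoint categorical percentages and later-period adverse event head-count percentages by (1 − d). At a true 25%, that costs 1.3, 2.5 or 5.0 points for 5%, 10% or 20% gone. With no attrition it costs nothing.

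A reader might go further and infer that the default favours CRD-740. That would need higher attrition on CRD-740, and the documents give no attrition in either arm. Equal attrition leaves the ratio between arms unchanged. Even the 3.8-point gap, from an assumed 20% against 5%, is less than one placebo subject (1/20 = 5 points). Nor do the documents support a claim that the primary safety analysis is compromised, since it rests on at-risk time.

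**What to change.** Add to SAP 6.1 or 6.7:

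- By-timepoint categorical percentages (laboratory and CTCAE shifts, ECG assessment, physical examination) use subjects assessed at that timepoint, and for shifts also with a baseline value.
- By-period adverse event percentages use Safety population subjects with at least one dose in that period.
- Each table shows the n used as denominator.
- By-period adverse event percentages are labelled descriptive, because they condition on having reached the period.

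The population denominator can stay for disposition and baseline tables. Where it departs from protocol 8.3, as in baseline tables with a Missing row, record that in section 7. If the shells already set these denominators, move the rule into the SAP text so that the two agree.

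The cost is a sentence or two in the SAP and footnotes in the shells. No new data are needed.

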#### 6.2. Subject Disposition and Data Sets Analyzed

Subject disposition will be summarized by treatment group, and overall for Part A of the study, where appropriate, for the All Screened Population. The following information will be reported:

- Number of subjects for the following categories:
  - o Screened,
  - o Treated but not randomized.

CONFIDENTIAL

- Number and percentage of subjects for the following categories:
  - o Randomized,
  - o Treated,
  - Not Treated,
  - o Discontinued the study treatment,
  - o Reasons for study treatment discontinuation
  - o Completed the study,
  - Ongoing in the study,
  - o Discontinued the Study,
  - o Reasons for study discontinuation.
- Number and percentages of subjects completing period 1, completing period 2 and completing period 3 (applicable for Part A only)
- Number and percentage of subjects included in, and excluded from, each study population together with the reasons for exclusion from the respective analysis population (this will be summarized for ITT population);
- Number and percentage of subjects who met / did not meet all eligibility criteria, together with the criteria not met;
- Number and percentage of subjects who failed screening prior to randomization, including the primary reason for screen failure;
- Number and percentage of subjects at each site (this will be summarized for ITT population);
- Number and percentage of subjects by stratification factors (this will be summarized for ITT population). Each stratification variable will be presented by the stratum collected in Interactive web-based response system (IWRS) and the stratum collected in the eCRF (if available).

In Part A of this study, a subject will be considered to have completed the study if he/she has answered "Yes" to question "Did the subject complete the study" on *Disposition – End of Study* form in eCRF. A subject will be considered as having discontinued the study if the question is answered "No". Otherwise, the subject will be considered as ongoing study.

A subject will be considered to have discontinued the study treatment if reason of discontinuation is provided on *End of Treatment* eCRF form.

A listing of all subjects with their treatment and study completion status, including the respective reasons for treatment and study discontinuation will be presented for the ITT.

A listing of all screen failed subjects with their reasons for screen failure will be presented for the All Screened Population. A separate listing of subjects who failed at least one inclusion /

2 Protocol Reference: CRD-740-201

CONFIDENTIAL

exclusion criteria including a text description of the criterion failed will be presented for the All Screened Population.

A listing of all randomized subjects with their randomization details, including first dose date and time, and actual treatment received will be presented for the ITT.

A listing of all subjects excluded from at least one analysis population will be presented for the All Screened Population.

#### **6.3. Protocol Deviations**

All important protocol deviations will be summarized for the ITT by treatment group and overall for Part A of the study as described below:

• The number of unique subjects with at least one important protocol deviation as well as the number of subjects in each important protocol deviation category will be presented by default descriptive summary statistics for categorical variables.

A listing of all subjects with one or more important protocol deviations will be presented for the ITT. In addition, a listing of the subjects affected by Coronavirus Disease of 2019 (COVID-19) and the type of COVID-19 disruption will be provided for the ITT.

#### 6.4. Demographic and Other Baseline Characteristics

## **6.4.1. Demographic Characteristics**

Demographic characteristics will be summarized for the ITT by treatment group and overall for Part A of the study as described below. All missing data will be presented as part of a missing category, if appropriate. Standard descriptive statistics will be presented for the continuous variables of:

- Age (years)
- Height (cm) at baseline
- Weight (kg) at baseline
- Body mass index (kg/m²) at baseline [calculated as (body weight / height²) where weight is in kg and height is in m] and presented to one decimal precision

Total counts and percentages of subjects will be presented for the categorical variables of:

- Age group (years):
  - 0 < 65
  - 0 > 65
- Sex (Male/Female)
- Reproductive system status (Childbearing potential, menopause status) for females only
- Race

CONFIDENTIAL Protocol Reference: CRD-740-201

• Ethnicity (Hispanic or Latino/Not Hispanic or Latino / Unknown)

In addition, a summary table presenting the number of subjects by geographical location (EU member state, Non-EU country, by each EU member state/Non-EU country) and overall for Part A. A further breakdown by age group and sex by geographical location may also be presented.

Countries will be retrieved from the 3 first digits of subject id as detailed in Table 5.

Table 5 Country and geographical locations from Subject number

Country	Range of the 3	Location
	first digits	
Bulgaria	101-149	EU member state
Canada	151-199	Non EU country
Czech Republic	201-249	EU member state
Hungary	251-299	EU member state
Israel	301-349	Non EU country
Italy	351-399	EU member state
Poland	401-449	EU member state
Slovakia	501-549	EU member state
United Kingdom	551-599	Non EU country
United States of America	601-649	Non EU country

Demographic characteristics will be listed for the ITT.

#### 6.4.2. Baseline Characteristics

Baseline characteristics will be summarized by treatment group and overall for Part A as described below. All missing data will be presented as part of a missing category, if appropriate.

Total counts and percentages of subjects will be presented for the categorical variables of:

- Echocardiogram performed during screening (Yes/No)
- EF group
  - o ≤40%
  - 0 > 40%

Standard descriptive statistics will be presented for the continuous variables of:

• EF (%) by EF subgroup ( $\leq 40\% / > 40\%$ )

Baseline characteristics will be listed for the ITT population.

### **6.4.3. Medical History**

Medical history is defined as any condition, with the exception of the study indication, that the subject may have had prior to enrollment in the study, including any chronic conditions diagnosed prior to entry in the study. See section 5.2.3 for imputation of missing or partial dates for medical history.

Medical history will be coded using the Medical Dictionary for Regulatory Activities (MedDRA) [version 24.1 or a later version if updated during the study] and will be presented by System Organ Class (SOC) and Preferred Term (PT). The SOCs and PTs are to be sorted by Internationally Agreed order SOCs and descending PTs in the overall column.

Medical history records will be summarized for the ITT population by treatment group and overall for Part A of the study as follows:

- The number and percentage of subjects with at least one medical history record will be presented.
- The number and percentage of subjects with at least one medical history record within each primary SOC and PT will be presented. The summary will be sorted using the internationally agreed order for SOC and using descending order of overall numerical counts for PT. Where terms tie, these will be sorted alphabetically.

Medical history records will be listed by-subject and within-subject by medical history start date for the ITT population.

